### 3 SUBJECT POPULATIONS

#### 3.1 Population Definitions

The following populations will be defined and used for analysis:

- x **Intent-to-Treat (ITT) Population:** The ITT population consists of all randomized subjects. This is the primary population for PFS and OS analysis. Subjects will be analyzed according to their randomized treatment assignment.
- x **Per-Protocol (PP) Population:** The PP population consists of all randomized subjects who do not have any protocol deviations that could confound the interpretation of the primary analyses conducted on the ITT population. The PP population will be used to perform sensitivity analysis for the primary efficacy endpoint PFS if the primary endpoint is statistically significant. Subjects will be analyzed according to their randomized treatment assignment.

Subjects with protocol deviations for any of the following criteria will be excluded from the PP population.

Eligibility criteria:

- x Subject must have a histologically- or cytologically-proven diagnosis of adenocarcinoma of the breast with evidence of either locally advanced disease not amenable to resection or radiation therapy with curative intent or metastatic disease not amenable to curative therapy (Protocol Inclusion Criteria 1)
- x Subject must have 1 of the following as defined by RECIST v1.1: (Protocol Inclusion Criteria 3)
  - o Measurable disease
  - o Bone only disease with evaluable lesions. Subjects must have at least 1 lytic or mixed lytic/blastic bone lesion; blastic lesions only are not evaluable and allowed.
  - o Subjects who have had prior radiation to bone must have at least 1 evaluable lesion in a nonirradiated area
- x Subject must have ER+ and HER2- tumor status confirmed per local laboratory testing (Protocol Inclusion Criteria 7)
- x Subject must have previously received at least 1 and no more than 2 lines of endocrine therapy, either as monotherapy or as a combination therapy with another agent for mBC (Protocol Inclusion criteria 8)
- x Subject must have progressed during or within 28 days of completion of prior treatment with a CDK4/6 inhibitor in combination with either fulvestrant or an AI for mBC (Protocol Inclusion Criteria 9)

Sponsor:	Radius		
Protocol:	RAD1901-308		
Document Version No.:	1.1 (Final)	Document Date:	10-MAY-2021

- x Subject must have received no more than 1 line of cytotoxic chemotherapy in the advanced/metastatic setting (Protocol Inclusion Criteria 10)
- x Subject must have an Eastern Cooperative Oncology Group (ECOG) performance status 0 or 1 (Protocol Inclusion criteria 11)
- x Subject must not have received prior treatment with elacestrant or investigational SERD or ER antagonist (Protocol Exclusion Criteria 1)
- x Subject must not have received prior anti-cancer or investigational drug treatment within the protocol defined window period (Protocol Exclusion Criteria 2)
- x Subject must not have difficulty in tolerating oral medications (Protocol Exclusion Criteria 12)
- x Subject must not have taken a moderate or strong CYP3A4 inhibitor or inducer 14 days prior to study entry or during the study (Protocol Exclusion Criteria 13)

Other criteria:

- x Subject did not provide main study informed consent
  - x Subject was randomized but did not receive any study drug
  - x Subject was treated with study drug they were not randomized to
  - x Subject received systemic anticancer therapy while on study drug
  - x Subject received radiation therapy to a target lesion
- x **Safety Population:** The Safety population consists of all subjects who received at least 1 dose of study drug. All safety analyses will be performed using the Safety population. Subjects will be analyzed according to the treatments they actually received in Cycle 1.
- x **Response Evaluable (RE) population:** The RE population includes all ITT subjects who had measurable disease (i.e., at least 1 target lesion) at baseline and at least 1 post-baseline RECIST assessment on any (target or non-target) lesions and/or had a new lesion. IRC-assessed RE population will be defined using IRC assessment while Local Investigator-assessed RE population will be defined using Local Investigator assessment.
- IRC-assessed ORR and DoR will be analyzed using IRC-assessed RE population. Local Investigator-assessed ORR and DoR will be analyzed using Local Investigator-assessed RE population.
- x **Clinical Benefit Evaluable (CBE) population:** The CBE population includes all ITT subjects who had measurable and/or evaluable disease (i.e., target and/or non-target lesions) at baseline and at least 1 post-baseline RECIST assessment on any (target or non-target) lesions and/or had a new lesion. IRC-assessed CBE population will be defined using IRC assessment while Local Investigator-assessed CBE population will be defined using Local Investigator assessment.

Sponsor:	Radius		
Protocol:	RAD1901-308		
Document Version No.:	1.1 (Final)	Document Date:	10-MAY-2021

---

IRC-assessed CBR will be analyzed using IRC-assessed CBE population. Local Investigator-assessed CBR will be analyzed using Local Investigator-assessed CBE population.

- x **Pharmacokinetic (PK) Population:** The PK population consists of all subjects who received at least 1 dose of elacestrant and have plasma elacestrant concentration data for at least 1 scheduled time point. PK analyses will be performed using the PK population.
- x **Biomarker Population:** The Biomarker population comprises all safety subjects for whom baseline and at least 1 post-baseline result are available for the biomarker of interest. The exploratory biomarker analysis will be performed using the Biomarker population.

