7. Any of the following within 6 months before enrollment: myocardial infarction, severe/unstable angina, ongoing cardiac dysrhythmias of NCI CTCAE v5.0 Grade ≥ 2 , prolonged QTcF \geq Grade 2 (ie, > 480 msec), uncontrolled atrial fibrillation of any grade, coronary/peripheral artery bypass graft, heart failure \geq Class II as defined by the New York Heart Association guidelines ([Appendix 6](#)), or cerebrovascular accident including transient ischemic attack
8. Child-Pugh Score greater than Class A (ie, score > 6; [Appendix 7](#))
9. Coagulopathy or any history of coagulopathy within the past 6 months, including history of deep vein thrombosis or pulmonary embolism. However, subjects with the following conditions will be allowed to participate:
 - a. Adequately treated catheter-related venous thrombosis occurring > 28 days prior to the first dose of study drug
 - b. Treatment with an anticoagulant, eg, warfarin or heparin, for a thrombotic event occurring > 6 months before enrollment, or for an otherwise stable and allowed medical condition (eg, well controlled atrial fibrillation), provided dose and coagulation parameters (as defined by local standard of care) are stable for at least 28

days prior to the first dose of study drug and provided that an AI would be an appropriate therapy for the subject

10. Known bleeding disorder which, in the opinion of the Investigator, would prohibit administration of fulvestrant if that would be SOC choice for the subject
11. Known difficulty in tolerating oral medications or conditions which would impair absorption of oral medications such as: uncontrolled nausea or vomiting (ie, CTCAE \geq Grade 3 despite antiemetic therapy), ongoing gastrointestinal obstruction/motility disorder, malabsorption syndrome, or prior gastric bypass
12. Unable or unwilling to avoid prescription medications, over-the-counter medications, dietary/herbal supplements (eg, St. John's wort), and/or foods (eg, grapefruit, pomelos, star fruit, Seville oranges and their juices) that are moderate/strong inhibitors or inducers of CYP3A4 activity ([Appendix 8](#)). Participation will be allowed if the medication, supplements, and/or foods are discontinued for at least 5 half-lives or 14 days (whichever is longer) prior to study entry and for the duration of the study
13. Major surgery < 28 days before the first dose of study drug

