9.1.3. Prohibited Medications

All subjects are prohibited from taking any of the following medications:

- Hormonal medications or medications known to affect serum luteinizing hormone (LH), FSH (except spironolactone which is allowed if medically indicated), or estrogen estradiol levels within 14 days (42 days for fulvestrant) of the first dose of study drug or anytime during the study. This includes, but is not limited to medications, herbal remedies, and/or supplements for the treatment of vasomotor hot flush symptoms administered via any route, including topical or intravaginal administration.
- Any systemic anti-cancer therapy or any other chemotherapeutic agents.
- Bisphosphonates and RANKL inhibitors to manage bone metastases are permitted only if the subject was receiving these agents and was on a stable dose for at least 3 months prior to first dose of study treatment; such agents should not be initiated during study treatment.
- In general, surgical tumor resection, tumor embolization, and radiation therapy are not permitted. Localized palliative radiation therapy may be permitted if no other option is available for pain management, only with approval of the Medical Monitor.

For Elacestrant Treatment Group:

- Medications, herbal preparations, supplements, and herbs or foods known to be moderate/strong inhibitors or inducers of CYP3A should not be used or consumed for the duration of the study because elacestrant undergoes biotransformation primarily by CYP3A. A more detailed listing of these products is provided in [Appendix 8](#)

For SOC Treatment Group:

- Refer to the PI or SmPC for complete information about potential drug interactions
- For subjects taking exemestane: CYP3A4 inducers may significantly decrease exposure. Therefore, medications and supplements that are known to be strong inducers of CYP3A4 should not be used/consumed for the duration of the study for subjects taking exemestane ([Appendix 8](#))

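### The SAP's per-protocol list misnumbers two exclusion criteria, shortens the CYP3A4 washout, and applies an on-study CYP3A4 rule on which the protocol contradicts itself

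*SAP*

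**What the plan says.** SAP Section 3.1 removes from PP any subject with a protocol deviation on a listed criterion. Four of the listed items are protocol exclusion criteria. Two concern us:

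- Oral tolerance: "Subject must not have difficulty in tolerating oral medications (Protocol Exclusion Criteria 12").
- CYP3A4 agents: "Subject must not have taken a moderate or strong CYP3A4 inhibitor or inducer 14 days prior to study entry or during the study", which the SAP attributes to Exclusion 13.

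In protocol Section 5.2, oral tolerance is Exclusion 11, CYP3A4 is Exclusion 12, and Exclusion 13 is "Major surgery < 28 days before the first dose of study drug". The synopsis uses the same order. On washout, Exclusion 12 says "Participation will be allowed if the medication, supplements, and/or foods are discontinued for at least 5 half-lives or 14 days (whichever is longer"), and the same sentence extends the avoidance through the whole study. Like every exclusion criterion, it is written for all subjects, before assignment.

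Protocol Section 9.1.3 instead splits the on-study restriction by arm. For the elacestrant group, moderate or strong CYP3A inhibitors and inducers "should not be used or consumed for the duration of the study because elacestrant undergoes biotransformation primarily by CYP3A". For the SOC group it refers to the product label, and the only CYP3A4 restriction it names concerns exemestane: "medications and supplements that are known to be strong inducers of CYP3A4 should not be used/consumed for the duration of the study for subjects taking" that drug.

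SAP Section 4.12.6 labels moderate and strong CYP3A4 inhibitors and inducers as prohibited and tabulates their use by treatment group and SOC type. SAP Section 6 declares that a PP population was added, but mentions no departure from the wording of Exclusion 12.

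**The concern.** A PP criterion should reproduce the protocol requirement that it enforces. Here the cited number points to a different criterion, the washout is not the protocol's, and the on-study clause depends on which of two protocol sections governs.

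Sensitivity Analysis 5 (SAP Section 4.7.1.3) repeats the primary PFS analyses in PP to check that deviations do not drive a positive result. If membership is set by a rule that differs from the protocol, that check loses some of its meaning. The on-study clause matters most. It acts after randomization, and Section 9.1.3 gives the two arms different instructions, so removals could differ between arms for reasons unrelated to adherence.

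**Working it through.** No sample size, power or alpha figure underlies this point. The check compares the two documents item by item, with one line of arithmetic for the washout.

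**1. Numbering** (SAP 3.1 against protocol 5.2)

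| Item in the PP list | SAP cites | Protocol number |
|---|---|---|
| Prior elacestrant, investigational SERD or ER antagonist | 1 | 1 |
| Prior anti-cancer therapy windows | 2 | 2 |
| Oral tolerance | 12 | 11 |
| CYP3A4 agents | 13 | 12 |

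Two of the four exclusion citations are wrong, each one too high. Read by number alone, the last two rows would select CYP3A4 (12) and major surgery (13) and would miss oral tolerance (11).

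**2. Washout** (t = half-life in days)

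- SAP: W_SAP = 14 days.
- Exclusion 12: W_prot = max(5t, 14) days.
- The two differ when 5t > 14, that is t > 14/5 = 2.8 days (67.2 hours).
- Gap = 5t − 14 days.

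The documents give no half-lives for these agents, so the following are assumed illustrations:

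- t = 2.8: 14 against 14, gap 0.
- t = 4: 20 against 14, gap 6 days.
- t = 7: 35 against 14, gap 21 days.

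A subject who stopped such an agent inside the gap breaks Exclusion 12 but satisfies the SAP criterion. The gap precedes treatment and does not depend on the assigned arm.

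**3. On-study use**

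| Treatment | Exclusion 12 | Protocol 9.1.3 | SAP PP rule |
|---|---|---|---|
| Elacestrant | moderate/strong inhibitors and inducers | same | same |
| Exemestane | same as above | strong inducers; otherwise product label | moderate/strong inhibitors and inducers |
| Fulvestrant, anastrozole, letrozole | same as above | none named; product label | moderate/strong inhibitors and inducers |

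The SAP column agrees with Exclusion 12 in every row. It is broader than Section 9.1.3 in both SOC rows. The conflict is therefore inside the protocol, and the SAP adopts one side without comment.

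**The case against.** The strongest reply is that these are drafting slips with little consequence.

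- **Numbering.** Each PP item is described in words, and SAP Section 3.2 has the sponsor finalize, before database lock, a file that describes every deviation and marks whether it excludes the subject. Nothing says that deviations are selected by criterion number. This stands: the wrong numbers are certain, but wrong removals are only possible.
- **Washout.** The gap is confined to long half-life agents, and the general PP definition and the sponsor's review could still remove such a subject. This also stands in part, but it leaves to discretion what the listed criterion should settle.
- **On-study rule.** The SAP follows Exclusion 12, which binds everyone, and removal requires a protocol deviation. If Exclusion 12 governs, SOC use is a deviation and the clause is consistent with it. If Section 9.1.3 governs, SOC use outside its limits is no deviation and the condition for removal is not met.

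That last argument defeats a stronger reading that a reader might infer: that the PP rule removes SOC subjects for drugs their arm is allowed to take. The documents do not establish this. Section 9.1.3 gives SOC subjects no express permission, and Exclusion 12 screens all subjects for willingness to avoid these agents.

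Two further inferences also fail. The washout gap does not single out elacestrant subjects, since it is the same in both arms. And the 5.27-fold rise in elacestrant AUC reported in protocol Section 2.2.2.1 comes from concurrent itraconazole, so it does not measure any residual effect of an agent stopped more than 14 days before entry.

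**Conclusion.** Two errors are shown by the text alone: two of four exclusion citations are off by one, and the CYP3A4 washout omits the half-life limb of Exclusion 12, with effect for agents whose half-life exceeds 2.8 days. A third matter is open rather than wrong: whether on-study CYP3A4 use in the SOC arm is a deviation that should remove a subject from PP. The SAP cannot settle that while Exclusion 12 and Section 9.1.3 disagree.

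The reach is small. PP feeds one efficacy analysis, Sensitivity Analysis 5 of PFS, which is run only if the primary endpoints are significant. The ITT primary analysis, alpha, power and OS are untouched.

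The number of subjects affected cannot be computed. A reader might take half of the 478 enrolled (239) as the SOC arm, assume that 5% to 15% used such an agent, and obtain 12 to 36 (0.05 × 239 and 0.15 × 239). No usage rate appears in the documents, and the count would also presuppose that Section 9.1.3 governs. It should not be relied on.

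**What to change.** Before the deviation file is finalized:

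1. In SAP Section 3.1, correct the citations to Exclusion 11 (oral tolerance) and Exclusion 12 (CYP3A4).
2. Replace the flat 14 days with the complete Exclusion 12 washout, and state which date counts as study entry.
3. Have the sponsor reconcile the whole-study clause of Exclusion 12 with the arm-specific text of Section 9.1.3. This review does not say which should prevail.
4. Then make the on-study PP criterion, and the label of these drugs as prohibited in SAP Section 4.12.6, follow the reconciled rule.

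Items 1 and 2 need no decision on item 3. The cost is SAP wording, the PP flag specification and a reference table of half-lives for the agents found. No new data collection is needed: prior and concomitant medications are already recorded from 35 days before consent to 30 days after the last dose (protocol Section 9.1.2). That look-back covers 5 half-lives for half-lives up to 35/5 = 7 days. For longer ones, coverage depends on the time from consent to entry, and the SAP should say so.

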### 3.2 Protocol Deviations

A major protocol deviation is defined as a deviation from basic requirements of the study protocol, including inclusion and exclusion criteria, concomitant medication restrictions, dosing (i.e., outside of  $\pm$  20% prescribed dose of study drug), or any protocol requirements that result in a significant added risk to the study participant or have an impact on the quality of the data collected or the outcome of the study. Major protocol deviations will be identified by Radius. The final list of Important Protocol Deviations that will exclude subjects from the PP populations will be imported to analysis data via an excel file. Major protocol deviations will be summarized by category, if applicable, and by treatment group in the ITT population. A by-subject data listing of all protocol deviations will also be provided.

At the discretion of the sponsor, major and important protocol deviations, as determined by a review of the data, may result in the exclusion of a subject's data from the PP population data set. The sponsor will be responsible for producing the final protocol deviation file (formatted as a Microsoft Excel file); this file will include a description of all protocol deviations, and clearly identify whether or not each deviation warrants exclusion from the PP population data set. This file will be finalized prior to database lock.

Sponsor:	Radius		
Protocol:	RAD1901-308		
Document Version No.:	1.1 (Final)	Document Date:	10-MAY-2021

---

## 4 STATISTICAL METHODS

### 4.1 Sample Size Justification

Note: This section describes the justification for the sample size used when the study was initiated and was based on PFS only. This amendment adds a truncated Hochberg procedure to allow testing of the key secondary endpoint of OS while maintaining the family-wise type I error rate at 5% (2-sided). At the time of this amendment, the study is fully enrolled (N=478) and the sample size will not be increased. Section 4.2.6 describes the testing procedures to be used for OS and the power associated with the OS analysis based on the number of OS events expected for the 478 subjects.

Among the ESR1-mut subjects, the study requires approximately 160 PFS events to have a power of 80% to detect a hazard ratio of 0.610 at the 2-sided alpha level of 2.5%. Assuming a median PFS of 5.3 months for the SOC treatment group, this treatment effect represents a median PFS of 8.7 months for the elacestrant treatment group, an increase of approximately 3.4 months among the ESR1-mut subjects.

Among all subjects (ESR1-mut and ESR1-mut-nd), a total of approximately 340 PFS events will have 92% power to detect a hazard ratio of 0.667 at the 2-sided alpha level of 2.5%.

The 2-sided alpha level of 2.5% for the sample size calculation is selected to ensure that at least 1 of the 2 primary efficacy endpoints will pass the Hochberg procedure ([Hochberg, 1988](#)) to control the overall alpha level at 5.0% (see Section 4.2.6).

The study will need to randomize approximately 220 ESR1-mut subjects (110/treatment group) and a total of approximately 466 subjects of both types (ESR1-mut and ESR1-mut-nd, 233/treatment group) in a 1:1 ratio to the two treatment groups.

To prevent exceeding the target recruitment by more than 10% (i.e., 512 subjects total), if a total of 292 ESR1-mut-nd subjects is reached before 220 ESR1-mut subjects are enrolled, further enrollment will be restricted to ESR1-mut subjects only until the target of 220 is achieved.

Final analysis of the primary endpoint will be performed at approximately 160 PFS events among the ESR1-mut subjects and 340 PFS events among all subjects (ESR1-mut and ESR1-mut-nd), estimated to occur at 30-33 months after the first subject is randomized.

### 4.2 General Statistical Methods and Data Handling

#### 4.2.1 General Methods

For continuous variables, descriptive statistics will include the number of subjects, mean, standard deviation, median, Q1, Q3, minimum, and maximum. For categorical variables, descriptive statistics will include the number of subjects, frequency counts and percentages. Time-to-event endpoints will be

Sponsor:	Radius		
Protocol:	RAD1901-308		
Document Version No.:	1.1 (Final)	Document Date:	10-MAY-2021

analyzed by the Kaplan-Meier method. When tabulating categorical data, “missing” will be included as a category and the number of subjects with missing data will be presented.

#### 4.2.2 Computing Environment

All descriptive statistical analyses will be performed using SAS statistical software (Version 9.4), unless otherwise noted. Medical History and adverse events will be coded using MedDRA version 23.0. Concomitant medications will be coded using World Health Organization (WHO) Drug version Sep2018.

#### 4.2.3 Reference Start Date, Baseline Definitions, and Study Day

Baseline is defined as the last non-missing assessment prior to or on the first dose date. For subjects who are randomized but not dosed, baseline is defined as the last non-missing assessment prior to or on the date of randomization.

All data listings that contain an evaluation date will contain a relative study day. Study day is defined as the number of days relative to the reference start date. The reference start date is designated as Study Day 1. Study Day -1 is the day that precedes Study Day 1. There is no Day 0 in this study. Study Day will be calculated as follows:

- x Before reference start date: Study Day = (Date of assessment – reference start date)
- x On or After reference start date: Study Day = (Date of assessment – reference start date) + 1
- x For efficacy assessments (tumor assessment, progression, death), the reference start date is date of randomization.
- x For other assessments, the reference start date is the first dose date. For subjects who did not take any study drug, the reference start date is date of randomization.

